5.9.1 Controlling for Multiplicity

No adjustments will be made for multiple comparisons.

5.10 SAFETY ANALYSES

All safety parameters will be analyzed descriptively for the Safety Population.

5.10.1 Adverse Events

Adverse events will be coded using the latest version of Medical Dictionary for Regulatory Activities (MedDRA) available at the start of the study. Treatment-emergent adverse events (TEAEs) are those AEs that started or worsened in severity after the administration of study drug. TEAEs will be summarized for each treatment group by SOC and PT; PT and severity, by SOC; PT and relationship to study drug; and by SOC, PT, and baseline eGFR. If a patient has more than 1 TEAE coded to the same preferred term, the patient will be counted only once for that preferred term by identifying those TEAEs with the highest severity and the closest relationship to study drug.

In addition, the incidence of AEs leading to premature discontinuation of study drug will be summarized by treatment group. Listings of pretreatment AEs, TEAEs, severe TEAEs, study drug-related AEs, SAEs, AEs leading to study discontinuation, and AEs leading to death (if any) will be provided.

5.10.2 Clinical Laboratory Parameters

Descriptive statistics for clinical laboratory values (in standard units) and changes from the baseline values at each assessment time point will be presented by treatment group for each clinical laboratory parameter.

5.10.3 Vital Signs

Descriptive statistics for vital signs (ie, pulse rate, systolic and diastolic BP, respiratory rate, temperature, and body weight) and changes from baseline values at each visit will be presented by treatment group for the Safety Population.

5.10.4 ECGs

Descriptive statistics for ECG parameters and changes from the baseline values at the end of treatment visit will be presented by treatment group for the Safety Population.

The number and percentage of patients with ECG abnormalities will be tabulated by treatment group. A listing of all AEs for patients with ECG abnormalities will also be provided.

5.10.5

[REDACTED]

[REDACTED]

[REDACTED]

[REDACTED]

[REDACTED]

[REDACTED]

[REDACTED]

5.11

PK

All PK analyses will be based on the PK Population. Descriptive statistics will be presented for IW-1973 plasma concentrations at each assessed timepoint.

[REDACTED]

[REDACTED]

[REDACTED]

[REDACTED]

[REDACTED]

5.12

[REDACTED]

[REDACTED]

[REDACTED]

5.13 DATA MONITORING COMMITTEE

An independent DMC will be given the responsibility to review trial safety and provide guidance consistent with the objectives of the study and appropriate ethical requirements.

The DMC will comprise experts in cardiovascular and/or renal disease, diabetes, and biostatistics, who have experience in clinical trials and are not involved in the conduct of this trial. Their only role in this study will be as a member of the DMC, thus ensuring their independent review of safety data.

Three safety review meetings will be scheduled: the first after 30 patients have been randomized, or 5 months after the first subject is randomized (whichever is earlier); the second after approximately 1/3 of patients have completed or discontinued treatment; and the third after approximately 2/3 of patients have completed or discontinued treatment.

For these periodic reviews, the DMC will be provided with summaries of all available AE and blood pressure data by treatment groups randomly masked as A, B, and C. An independent statistician will be responsible for summarizing and submitting these safety data to members of the DMC. All data presentations for the DMC will be performed using the Safety Population. If a safety/tolerability signal or concerning AE imbalance is identified at a review, the committee can request unblinding of the masked treatment groups as well as additional safety data. At each meeting, the DMC will review accumulated AE data and recommend trial continuation, modification, or termination. The DMC will also be required to perform an ad hoc review if 2 or more study drug-related SAEs from 1 category in [Table 3](#) are reported. In this circumstance, the committee will be provided with narrative descriptions and all relevant clinical supporting

documentation related to the SAEs. Upon request, the unblinded treatment and dose the subjects received will be provided to the committee.

In addition to the periodic and ad hoc reviews, during the trial, committee members will be provided with blinded reports on all SAEs.

The DMC or the Sponsor may request ad hoc meetings at any time and at their discretion.

There are no predefined stopping rules for the trial (for individual stopping rules, see Section 3.7.1). However, the DMC will be reviewing safety data as described above. The Sponsor, upon the recommendation of the DMC, may stop the study at any time for significant safety concerns. If the DMC recommends stopping or modifying the trial, a senior review team from the Sponsor will have the opportunity to review the blinded data and discuss study findings with the DMC. The senior review team will be separate from the study project teams. The Sponsor may also seek input from relevant regulatory authorities. The Sponsor will make the final decision on the recommendation and will relay its decision to the DMC and relevant regulatory authorities. Additional details will be provided in the DMC charter, which will be developed in collaboration with the DMC members and will be finalized before trial initiation.

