Symptomatic hypotension-related events (eg, syncope)	2

DMC=Data Monitoring Committee; eGFR=estimated glomerular filtration rate; SAE=serious adverse event

Individual

On an individual basis, a patient will be discontinued from study drug dosing if 1 or more SAEs from the table is reported. At the Investigator's or Sponsor's discretion, any AE(s) of concern can likewise be the basis for patient discontinuation from the trial.

Study

An independent DMC will review trial safety data. The DMC will comprise experts in cardiovascular and/or renal disease and/or diabetes and a biostatistician who have experience in clinical trials and are not involved in the conduct of this trial.

Periodic safety review meetings will be scheduled after 30 subjects have been randomized or 5 months after the first subject is randomized (whichever is earlier) and when approximately 1/3 and 2/3 of patients have completed or discontinued treatment. The committee will review accumulated AE data and recommend trial continuation, continuation with modification, or termination. For these periodic reviews, the DMC will be provided with summaries of AE and blood pressure data. If a safety/tolerability signal or concerning AE imbalance is identified at a review, the committee can request unblinding of the masked treatment groups and may request additional safety data (eg, vital signs, concomitant medications).

The DMC will also be required to perform an ad hoc review if SAEs from the same category in the above table are reported at the incidence indicated in the table shown above (eg, 2 patients with spontaneous bleeding SAEs). In this circumstance, the DMC will be provided with narrative descriptions and all relevant clinical supporting documentation related to the SAEs. Upon request, the unblinded treatment codes and dose the subjects with the SAEs received will be made available to the committee.

In addition to the periodic and ad hoc reviews, during the trial, committee members will be provided with blinded reports on all SAEs. The DMC or the Sponsor may request ad hoc meetings at any time.

Final decision-making authority regarding study conduct will rest with the Sponsor. Additional details will be provided in the DMC charter, which will be developed in collaboration with the DMC members and will be finalized before the first patient is randomized.

Study Assessments

All study assessments will be performed according to the [Schedule of Events](#).

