3.5.6 Blinding

This study is double blind and placebo controlled. The investigational product and placebo will be identical oral tablets.

Unblinding of a patient's treatment assignment is restricted to emergency situations and should only be used under circumstances where knowledge of the treatment is necessary for the proper handling of the patient. Except in a medical emergency, the Investigator and study center staff will remain blinded during the conduct of the study and until, at a minimum, all discrepancies in the clinical database are resolved (ie, at the time of the database lock). Individual patient treatment assignment unblinding is available to the Investigator through the interactive web response system (IWRS) in the event of an emergency. The Investigator should make all reasonable efforts to notify and discuss the circumstances requiring unblinding with the Medical Monitor or designee in advance of breaking the blind. If the treatment blind is broken, the reason and the date should be recorded and signed by the Investigator and information regarding the unblinding should be submitted as soon as possible to the Sponsor. If the Investigator is unblinded to the treatment assignment of a patient, the patient will be immediately withdrawn from study drug dosing and should follow early termination procedures (Section [3.4.3](#)).

The Sponsor may also break the blind in circumstances where unblinding is necessary for the safety of the patients.

To allow ongoing safety monitoring during the conduct of the study, members of an external DMC will review summaries of AE data by treatment groups randomly masked as A, B, and C and may request unblinded safety data. Please refer to Section [5.13](#) for more details.

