3.7 INDIVIDUAL STOPPING CRITERIA AND DMC REVIEWS

If any events included in [Table 3](#) are reported during the study and are judged to be both study drug related and an SAE (per causality and SAE definitions in Section [3.8.9.3](#)), individual stopping criteria or DMC review will be triggered per the criteria in Sections [3.7.1](#) and [Table 3](#), respectively. The inclusion of these AEs is based on the clinical experience with IW-1973, the prescribing information for riociguat, and the patient population for this study.

Table 3. Categories of SAEs Triggering Individual Stopping Criteria and Safety Committee Review

Treatment-emergent Study Drug-related SAE Category	# of patients to trigger DMC review
Renal failure (eGFR <15 mL/min/1.73 m ² ; dialysis or renal transplant indicated)	2
Spontaneous bleeding events (eg, hemoptysis, subarachnoid or subdural hemorrhage, hematemesis, hematochezia)	2
Symptomatic hypotension-related events (eg, syncope)	2

DMC=Data Monitoring Committee; eGFR=estimated glomerular filtration rate; SAE=serious adverse event

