3.8.9.4 Recording Adverse Events

Adverse events will be collected and recorded from the time the patient signs the ICF at the Screening Visit through the Follow-up Visit. All AEs, regardless of the assumption of a causal relationship with study procedures or study medication, must be recorded in the patient's source documentation and subsequently on the appropriate AE page of the patient's eCRF. This record includes AEs the patient reports spontaneously, those observed by the Investigator, and those elicited by the Investigator in response to open-ended questions during the study, such as "Have you had any health problems since your last visit?"

For every AE, the Investigator must:

- Provide an assessment of the severity, causal relationship to the study medication, and seriousness of the event
- Document all actions taken with regard to the study medication (ie, no action taken, treatment temporarily interrupted, or treatment discontinued)
- Detail any other treatment measures taken for the AE, including concomitant medications and/or procedures

Pretreatment AEs will be collected from the time the patient signs the ICF until the patient receives study drug. Pretreatment AEs will be captured in the patient's source documentation but will only be entered for randomized patients on the AE page of the patient's eCRF.

Laboratory abnormalities and changes in vital signs, physical examination findings, and 12-lead ECG parameters should be considered AEs and reported on the AE page of the patient's eCRF if the Investigator considers them clinically significant and/or they necessitate intervention.

Any medical condition that is present when a patient is screened and does not worsen in severity and/or frequency should be reported as Medical History and not as an AE. However, if the condition does deteriorate in severity and/or frequency at any time during the study, it should be reported as an AE.

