3.9.2.2 Week 1 Visit (Day 8 ± 1)

- Return by patient:
 - 2 first-void urine samples

- Study drug (Patients will bring in study drug dispensed on Day 1. MEMS Caps will be read, and the subject will be administered the Day 8 [± 1] study drug dose in the clinic from the Day 1 bottles. The subject will continue to dose from the Day 1 bottles until returning for the Week 4 Visit.)
- Collect predose urine samples for pregnancy test, as applicable
- Record concomitant medications
- Record weight
- Record respiratory rate and oral temperature predose (≤ 30 minutes)
- Record seated-to-standing (orthostatic) pulse and BP predose (≤ 30 minutes)
- Collect predose (≤ 30 minutes) blood samples for:
 - Serum creatinine and glucose
 - Hemoglobin A1c
 - Fasting plasma glucose and insulin
 - [REDACTED]
 - PK
- Review MEMS cap data
- Administer study drug
- Record respiratory rate and oral temperature at 1 hour (± 15 minutes) postdose
- Record seated-to-standing (orthostatic) pulse and BP at 1, 2, 4 and 6 hours (± 15 minutes) postdose
- Collect blood samples for PK at 1, 3, and 6 hours (± 15 minutes) postdose
- [REDACTED]
- Conduct AE evaluation
- Issue supplies and instructions for first-void urine sampling

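### The periodic DMC package is limited to adverse event and blood pressure summaries, so a moderate between-arm fall in eGFR would not routinely be shown at the three scheduled reviews

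*Protocol*

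**What the plan says.** - **Periodic package.** Section 5.13 schedules three reviews: after 30 patients are randomized or 5 months after the first randomization, whichever is earlier, and when about one third and two thirds of patients have completed or discontinued treatment. For these, "the DMC will be provided with summaries of all available AE and blood pressure data", by groups masked as A, B and C. The synopsis agrees: "the DMC will be provided with summaries of AE and blood pressure data". Section 3.5.6 is shorter: DMC members "will review summaries of AE data by treatment groups randomly masked as A, B, and C and may request unblinded safety data", with a pointer to 5.13.
- **Further data.** In 5.13 and the synopsis, a request for more data follows a signal or an adverse event imbalance seen at a review. The synopsis says the committee "may request additional safety data (eg, vital signs, concomitant medications"). These are examples, and no laboratory item is among them.
- **Reliance on the review.** Section 5.13 sets no predefined stopping rules for the trial and adds that "the DMC will be reviewing safety data as described above". Further detail is left to the DMC charter.
- **Renal data collected.** "Serum creatinine and glucose" are drawn at Randomization, Week 1 and Week 8 (3.9.2.1, 3.9.2.2, 3.9.2.4). At Week 4 and End of Treatment, creatinine is part of serum chemistry (3.9.2.3, 3.9.2.5, Table 4). Section 3.8.8.4 derives eGFR from it.
- **How a laboratory change becomes an adverse event.** Under 3.8.9.4, it does so "if the Investigator considers them clinically significant and/or they necessitate intervention".
- **Renal trigger.** The Table 3 renal category is a study drug-related SAE of renal failure, described as eGFR below 15, "dialysis or renal transplant indicated". Two patients trigger an ad hoc review.

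**The concern.** Table 3 names three risks: renal failure, bleeding and symptomatic hypotension. For hypotension, the routinely measured precursor (blood pressure) is in the periodic package. For renal failure, the corresponding measurement (creatinine, hence eGFR) is not, although it is collected on the same visit schedule.

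The population makes this matter. Patients start with eGFR 30 to 75, take an ACE inhibitor or ARB, and are given a drug that section 3.5.3 reports to lower blood pressure. Safety is a primary objective. A modest fall in mean eGFR in one arm is the kind of change that no single investigator need find clinically significant in any one patient, but that a by-arm table would show. With no predefined trial stopping rules, protection rests on what the DMC is given to read.

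**Working it through.** The protocol states no figure on this point, so there is none to reproduce. The check has three parts.

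**1. Is arm-level renal data supplied anywhere as a matter of routine?**

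| Route | What the protocol provides | Routine by-arm eGFR? |
|---|---|---|
| Periodic package (5.13, synopsis) | Adverse events, blood pressure | No |
| Blinding section (3.5.6) | Adverse events; unblinded safety data on request, no precondition stated | No, needs a request |
| Adverse event tables | Laboratory changes only if the investigator judges them significant or they need intervention (3.8.9.4) | No |
| SAE reports to the DMC (5.13) | Blinded reports on all SAEs | No |
| Ad hoc review (3.7, 5.13) | Two related SAEs in one Table 3 category; narratives | No |
| Ad hoc meetings (5.13) | At any time, at DMC or sponsor discretion | No, needs a decision to meet |
| Charter | Not shown | Unknown |

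**2. How far is the Table 3 renal category from a moderate fall?** Loss needed to reach eGFR 15 = 1 − 15/entry value:

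- from 30: 1 − 15/30 = 50%
- from 52.5, the middle of the entry range (30 + 75)/2: 1 − 15/52.5 = 71%
- from 75: 1 − 15/75 = 80%

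**3. Would a by-arm eGFR table be informative at these sample sizes?**

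Inputs: about 150 patients randomized 1:1:1 (5.2), and the review times in 5.13. Per arm this gives at most about 30/3 = 10 at the first review, then 50/3 ≈ 17 and 100/3 ≈ 33. The SD of eGFR change is not in the protocol; a range of 6 to 10 mL/min/1.73 m² is **assumed**.

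Half-width of the 95% CI for one arm against another = t(0.975, 2n − 2) × SD × √(2/n).

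| Review | n per arm | t | √(2/n) | SD 6 | SD 10 |
|---|---|---|---|---|---|
| First | 10 | 2.101 | 0.447 | 5.6 | 9.4 |
| One third | 16.7 | 2.039 | 0.346 | 4.2 | 7.1 |
| Two thirds | 33.3 | 1.997 | 0.245 | 2.9 | 4.9 |

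Between-arm falls from 52.5: 10% = 5.25; 15% = 7.88.

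- The 15% fall exceeds the half-width at the one-third review (4.2 to 7.1) and the two-thirds review (2.9 to 4.9) over the whole assumed SD range.
- The 10% fall exceeds it over the whole range only at the two-thirds review.
- At the first review, neither does so over the whole range, and many patients will have early visits only.

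**The case against.** **The charter.** The strongest point is that the protocol defers DMC detail to a charter, where table lists often sit, and 5.13 does not say that the package is adverse events and blood pressure only. The charter may well contain laboratory tables. This stands as a limit: the finding concerns what the protocol states, not what the DMC received. But the protocol does not leave the content open. It lists it twice, and both lists omit renal data.

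**Other routes.** The DMC may ask for safety data (3.5.6 sets no precondition), may meet at any time, and draws on cardiovascular and/or renal expertise; significant creatinine rises appear as adverse events. All true, but each needs a request or an investigator's judgement, and a silent eGFR shift may prompt neither.

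**Section 3.5.6.** It is a brief blinding paragraph that refers to 5.13, so its shorter list is a minor matter of alignment rather than a serious contradiction. Agreed.

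**Detectability.** Exceeding the half-width is not high power. At SD 10, two-sided power at the 5% level is about 60% for the 15% fall at the one-third review and about 56% for the 10% fall at the two-thirds review. Counting only Week 12 completers under the protocol's 20% drop-out gives 0.8 × 16.7 ≈ 13 and 0.8 × 33.3 ≈ 27 per arm. At SD 10 the half-widths are then about 8.0 and 5.5, slightly above 7.88 and 5.25. This qualifies the numbers at the upper end of the SD range. Against it, patients who stop early have End of Treatment laboratory tests (3.4.3), and patients still on treatment contribute earlier visits.

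**Table 3.** The eGFR threshold was meant for severe events, not mean shifts. Correct; the percentages show only that this trigger cannot stand in for a periodic eGFR table.

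**Separation from efficacy.** Renal function is a primary objective and the exploratory endpoints are redacted, so eGFR may also serve as an efficacy variable. That cannot be excluded. The stated primary efficacy endpoint is UACR, however, and the synopsis lists eGFR among the clinical laboratory assessments, which section 5.10 analyses as safety.

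**Conclusion.** The concern holds. As written, the periodic DMC package contains no creatinine or eGFR summary, and no other route in the protocol supplies one by arm as a matter of course. Under the assumed SD of 6 to 10, such a table would be of limited use at the first review. At the later two it could show falls of about 15% and 10% respectively from mid-range entry eGFR, with only moderate power at the upper end of that SD range. The conclusion about the text does not depend on the SD; the estimate of benefit does. The charter is unseen and may already close the gap. This is a worthwhile, low-cost correction to a stated list, not a flaw in the primary analysis.

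**What to change.** In section 5.13 and the synopsis, add to each periodic package summaries of serum creatinine and eGFR by masked group (A, B, C): value and change from baseline by visit, and counts of patients with categorical falls. Leave UACR out, so that the DMC review remains separate from the primary efficacy endpoint. Bring section 3.5.6 into line with the same list, and confirm that the charter matches.

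The cost is a few more tables from the independent statistician who already prepares the masked summaries. No new assessment, sample size change or alpha adjustment is needed. Laboratory data must be transferred in time for each meeting, and the first review will have limited data.

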5.14 INTERIM ANALYSIS (OPTIONAL)

After at least one half of the subjects ($N \geq 75$) have completed the last visit, an interim analysis to review unblinded efficacy data may be performed to assist with the planning of future studies. If performed, details regarding the interim analysis will be included in the SAP, along with updates to the data management plan as necessary. The independent statistician (who will not be involved in study data collection or interpretation) performing the interim analysis and Ironwood staff members, as identified in the SAP, may be unblinded. DMC reviews of safety data will be independent of this possible interim analysis of efficacy.

5.15 CHANGES IN THE CONDUCT OF THE STUDY OR PLANNED ANALYSES

Any amendment to this protocol will be provided to the Investigator in writing by Ironwood or its designee. Before implementation, any protocol amendment regarding reportable deviations (as defined by the IRB) must be approved by the IRB and the signature page must be signed by

the Investigator and received by Ironwood or its designee, with the following exception: If the protocol is amended to eliminate or reduce the risk to patients, the amendment may be implemented before IRB review and approval. However, the IRB must be informed in writing of such an amendment, and approval must be obtained within reasonable time limits.

Deviating from the protocol is permitted only if absolutely necessary for the safety of the patients and must immediately be reported to Ironwood or its designee.

